5.3.1.4 Time Between First and Second Trial Vaccine Dose

The time between the first and second trial vaccine dose (days) will be calculated as follow:

$$\text{Date of second trial vaccine dose} - \text{Date of first trial vaccine dose} + 1.$$

5.3.2 Efficacy

5.3.2.1 Fold Increase

The fold increase is calculated by taking the ratio of a subject's Visit 2 and Visit 4 assessments. If v_2 is a subject's Visit 2 record and v_4 is a subject's Visit 4 record then the fold increase is:

$$fi = \frac{v_4}{v_2}.$$

5.3.2.2 Seroresponse Rate

Seroresponse is defined as a fold increase from baseline (Visit 2) greater than or equal to 4.

Seroresponse rate (SRR) is defined as the percentage of subjects with a seroresponse.

5.3.2.3 Immunogenicity Assessments

When summarizing immunogenicity assessments the following rules will apply:

- If a record is below the lower limit of detection (LLOD) then 1/2 the LLOD value will be used in the summary
- If a record is below the lower limit of quantification (LLOQ) then the midpoint of the LLOQ value and the LLOD value will be used in the summary

- If a record is above the upper limit of quantification (ULOQ) then the ULOQ will be used in the summary

The following table gives the LLOD's, LLOQ's and ULOQ's for each of the parameters to be assessed on the study.

Table 2: Limits of Detection and Ranges of Quantification for Immunogenicity Assays

Parameter	LLOD	LLOQ	ULOQ
Diphtheria (DT)	0.000010 IU/mL	0.000037 IU/mL	0.005 IU/mL
Tetanus (TT)	0.000038 IU/mL	0.00005 IU/mL	0.041 IU/mL
Polio Type 1	2.50 log ²	N/A	N/A
Polio Type 2	2.50 log ²	N/A	N/A
Polio Type 3	2.50 log ²	N/A	N/A
Hepatitis B (HBsAg)	NA	10 mIU/mL	14043.4 mIU/mL
Pertussis Filamentous Hemagglutinin (FHA)	0.0009 IU/mL	0.0029 IU/mL	1.97 IU/mL
Pertussis Pertactin (PRN)	0.0007 IU/mL	0.003 IU/mL	0.7 IU/mL
Pertussis Toxoid (PT)	0.0004 IU/mL	0.0009 IU/mL	0.29 IU/mL
Haemophilus influenzae type B (PRP)	NA	0.15 µg/mL	28.55 µg/mL
Pneumococcal serotype 1	0.01 µg/mL	0.05 µg/mL	65.63 µg/mL
Pneumococcal serotype 3	0.01 µg/mL	0.05 µg/mL	21.82 µg/mL
Pneumococcal serotype 4	0.01 µg/mL	0.04 µg/mL	22.21 µg/mL
Pneumococcal serotype 5	0.01 µg/mL	0.06 µg/mL	66.32 µg/mL
Pneumococcal serotype 6A	0.01 µg/mL	0.04 µg/mL	67.98 µg/mL
Pneumococcal serotype 6B	0.01 µg/mL	0.07 µg/mL	61.05 µg/mL
Pneumococcal serotype 7F	0.01 µg/mL	0.08 µg/mL	94.95 µg/mL
Pneumococcal serotype 9V	0.01 µg/mL	0.08 µg/mL	52.87 µg/mL
Pneumococcal serotype 14	0.01 µg/mL	0.07 µg/mL	352.99 µg/mL
Pneumococcal serotype 18C	0.01 µg/mL	0.04 µg/mL	33.8 µg/mL
Pneumococcal serotype 19A	0.01 µg/mL	0.05 µg/mL	86.91 µg/mL
Pneumococcal serotype 19F	0.01 µg/mL	0.06 µg/mL	471.56 µg/mL
Pneumococcal serotype 23F	0.01 µg/mL	0.07 µg/mL	92.83 µg/mL
Rotavirus	5.76 U/mL	7.5 U/mL	N/A
Norovirus HBGA CN (GI.1)	19 AU/mL	19 AU/mL	78848 AU/mL
Norovirus HBGA NW (GII.4)	33 AU/mL	33 AU/mL	149504 AU/mL

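### The SAP's two substitution rules overlap below the LLOD, and under the natural reading an infant below the limit at Visit 2 counts as a 4-fold norovirus seroresponder at only twice the limit

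*SAP*

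**What the plan says.** SAP Section 5.3.2.3 introduces its rules with "When summarizing immunogenicity assessments the following rules will apply". The first reads "If a record is below the lower limit of detection (LLOD) then 1/2 the LLOD value will be used in the summary". The second covers any record below the LLOQ: "then the midpoint of the LLOQ value and the LLOD value will be used in the summary". No order of precedence is given, and the second rule has no lower bound.

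Table 2 in the same section lists LLOD, LLOQ and ULOQ in that order. For both norovirus assays the first two are equal: "Norovirus HBGA CN (GI.1) 19 AU/mL 19 AU/mL 78848 AU/mL" and "Norovirus HBGA NW (GII.4) 33 AU/mL 33 AU/mL 149504 AU/mL".

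Section 5.3.2.1 defines the fold increase as Visit 4 over Visit 2: "The fold increase is calculated by taking the ratio of a subject's Visit 2 and Visit 4 assessments". Section 5.3.2.2 then states: "Seroresponse is defined as a fold increase from baseline (Visit 2) greater than or equal to 4". Neither section has a rule for a Visit 2 titer below the limit, and neither says whether substituted values enter the ratio. SRR and GMFR for GI.1 and GII.4 are secondary endpoints (Sections 4.2.2 and 9.2.1.2), and Section 9.2.1.3 restricts their analysis to HIL-214 recipients.

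**The concern.** There are two separate problems.

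The first is wording. A record below the LLOD is also below the LLOQ, so the text assigns it two different values.

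The second remains when the wording is read sensibly. A result below the limit is known only to lie somewhere under it. Once it is fixed at half the limit, a Visit 4 titer of twice the limit gives a ratio of exactly 4, although the measurements establish only that the titer more than doubled. Norovirus is where this matters, because it is the only antigen with a fold-rise endpoint. No between-arm contrast is planned for SRR or GMFR, so the constant cannot cancel: it goes directly into the reported figure. Under Section 7.6.2 the HIL-214 immunogenicity data are withheld from the blinded analysis team until database lock. A choice left open until then would be made with results in view.

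**Working it through.** **Inputs** (SAP Table 2): LLOD = LLOQ = 19 AU/mL for GI.1 and 33 AU/mL for GII.4. Seroresponse: v4/v2 of at least 4. The SAP states no titer distribution or expected SRR, so there is no planned figure to reproduce.

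**Step 1: size of the overlap.** Half-LLOD rule: LLOD/2. Midpoint rule: (LLOD + LLOQ)/2. Their ratio is 1 + LLOQ/LLOD.

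| Assay | Half-LLOD | Midpoint | Ratio |
|---|---|---|---|
| GI.1 (AU/mL) | 9.5 | 19 | 2.0 |
| GII.4 (AU/mL) | 16.5 | 33 | 2.0 |
| Rotavirus (U/mL) | 2.88 | 6.63 | 2.3 |
| Pneumococcal 7F (µg/mL) | 0.005 | 0.045 | 9.0 |

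The overlap exists wherever both limits are given. Norovirus has the smallest ratio.

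**Step 2: Visit 4 titer needed when Visit 2 is below the limit L.** This is 4 times the substituted baseline.
- Half-LLOD: 4 x 9.5 = 38 = 2 x 19 (GI.1); 4 x 16.5 = 66 = 2 x 33 (GII.4).
- Midpoint: 4 x 19 = 76 (GI.1); 4 x 33 = 132 (GII.4).

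An infant measured at exactly 19 AU/mL at Visit 2 needs 76 AU/mL. One just below 19 needs 38 under the half-LLOD rule.

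**Step 3: what the data demonstrate.** If v2 < L and v4 = 2L, then v4/v2 > 2. The true rise is 4-fold or more only if the true baseline is at or below L/2. GI.1 examples under the half-LLOD rule:
- True baseline 18, Visit 4 38: true rise 38/18 = 2.1, counted as a seroresponse.
- True baseline 4.75, Visit 4 28.5: true rise 28.5/4.75 = 6, but 28.5/9.5 = 3, so not counted.

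The rule can misclassify in both directions.

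**Step 4: gap between cut-offs 2L and 4L.** This equals the share of HIL-214 infants with Visit 2 below L and a Visit 4 titer from 2L to under 4L. Assume that all infants are below the limit at Visit 2 and that Visit 4 titers are lognormal. Then gap = Φ((ln GMT − ln 2L)/SD) − Φ((ln GMT − ln 4L)/SD).

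For GI.1 at GMT 100 and ln-SD 1.0: Φ(0.968) − Φ(0.274) = 83.3% − 60.8% = 22.5 points.

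SRR under cut-offs 2L and 4L at ln-SD 1.2 (gaps from unrounded values):

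| Visit 4 GMT | GI.1: 38 v 76 | Gap | GII.4: 66 v 132 | Gap |
|---|---|---|---|---|
| 50 | 59.0% v 36.4% | 22.7 | 40.9% v 20.9% | 19.9 |
| 100 | 79.0% v 59.0% | 20.0 | 63.5% v 40.9% | 22.7 |
| 200 | 91.7% v 79.0% | 12.7 | 82.2% v 63.5% | 18.7 |
| 400 | 97.5% v 91.7% | 5.8 | 93.3% v 82.2% | 11.1 |

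Over GMT 50 to 400 and ln-SD 1.0 to 1.5, the gap is 3.9 to 27 points (GI.1) and 9.8 to 27 points (GII.4). Over GMT 50 to 800 and ln-SD 0.8 to 1.6 it runs from 0.2 to 33 points across the two assays. If only half the infants were below the limit at Visit 2, with the same Visit 4 distribution among them, 22.5 points would become 11.25.

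**Step 5: GMFR.** If the midpoint were used in place of half the LLOD, the GMFR would fall by a factor 2^f, where f is the share below the limit at Visit 2 and quantifiable at Visit 4: 2^0.5 = 1.41, 2^0.8 = 1.74. Infants below the limit at both visits have a ratio of 1 either way.

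**The case against.** The strongest reply is that the rules have only one sensible reading. If the midpoint rule overrode the half-LLOD rule, the latter would never operate in an assay with both limits. Only a tiered reading gives each rule a function, and for norovirus there is then nothing between the limits, so half the LLOD applies. This stands. The overlap is a drafting gap, and the GMFR factors in Step 5 arise only if the tiered reading is not followed. But the reply does not touch the second problem, which arises under the tiered reading itself.

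A reader might infer that the planned SRR is inflated, or that such seroresponses are produced by the substituted number. The documents do not support that. True baselines below the limit are unknown, half-LLOD is a convention and not an error, and Step 3 shows that it can also miss true 4-fold rises.

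A reader might also infer that 4 x LLOQ should replace the planned definition. That would be another convention: a GI.1 rise from 8 to 64 AU/mL, 8-fold, would be a non-response because 64 is below 76. It would also separate seroresponse from the fold increase that defines it.

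Nor does equality of the two limits cause the overlap; it only sets the factor at 2.

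The consequence is limited. The trial is descriptive (Section 6), these endpoints are secondary, counts below LLOD and LLOQ are reported (Section 9), and distribution curves are planned (Section 9.2.1.3). Those outputs show how many values are substituted, but they do not give the SRR under another cut-off. For rotavirus, 20% of records below the LLOD would move an arm's GMC by 2.30^0.2 = 1.18 between the two rules. The primary summary is a ratio of GMCs, so equal shares in the two arms cancel.

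**Conclusion.** The point holds in two parts. The midpoint rule lacks a lower bound, so Section 5.3.2.3 gives two values for any record below the LLOD in every assay with both limits. And under the natural reading, a norovirus seroresponse from a below-limit baseline requires only 38 or 66 AU/mL, which demonstrates a rise above 2-fold. The SRR can therefore overstate or understate true 4-fold responses, and the plan does not show how far it depends on the constant.

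The 4 to 27 points (GI.1) and 10 to 27 points (GII.4) measure the distance between two conventions, not the error of the planned one. They assume that substituted values enter v4/v2, that every infant is below the limit at Visit 2, and that Visit 4 titers are lognormal over the assumed range. The documents give neither the undetectable share nor the titer distribution. The gap falls in proportion to that share and becomes small at high GMTs. The change is worth making, but no primary conclusion depends on the seroresponse issue.

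**What to change.** 1. In Section 5.3.2.3, restrict the midpoint rule to records with LLOD <= record < LLOQ. This settles precedence for all assays with both limits and changes no norovirus result under the tiered reading.
2. In Section 5.3.2.1, state that substituted values enter v4/v2.
3. Keep the planned seroresponse definition. Add a pre-specified sensitivity SRR in which infants with Visit 2 below the LLOQ need a Visit 4 titer of at least 4 x LLOQ (76 AU/mL for GI.1, 132 AU/mL for GII.4). Label it a lower bound of demonstrated 4-fold rises, and report it beside the planned SRR.

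The cost is one clause, two sentences and one more table, with no new data. The downside for the sponsor is that a less favourable SRR may stand next to the planned one. The change should be made before the HIL-214 immunogenicity data are released to the analysis team.

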4.2 Study Endpoints and Estimands

4.2.1 Primary Endpoints and Estimands

Primary Immunogenicity Estimands:

Population:

Healthy infants 4 months of age, who meet all the trial eligibility criteria and who are to receive routine pediatric vaccines (DTaP-Hib-IPV-HepB, RV1, and PCV13) at 2, 4 and 6 months of age.

Treatment strategies to be compared:

- 2-dose series of HIL-214 at 4 and 6 months of age, with concomitant routine pediatric vaccines at 2, 4 and 6 months of age.

- 2-dose series of placebo at 4 and 6 months of age, with concomitant routine pediatric vaccines at 2, 4 and 6 months of age.

Primary immunogenicity endpoints (at 28 days post-dose 2 of HIL-214, administered at 6 months of age):

- Binary (yes/no) variable indicating anti-DT IgG concentration ≥ 0.1 IU/mL.
- Binary variable indicating anti-TT IgG concentration ≥ 0.1 IU/mL.
- Anti-FHA, PRN, and PTX IgG concentrations.
- Binary variable indicating anti-poliovirus neutralizing antibody titers $\geq 1:8$, for poliovirus types 1, 2 and 3.
- Binary variable indicating anti-PRP IgG concentration ≥ 0.15 μ g/mL.
- Binary variable indicating anti-HBsAg Ig concentration ≥ 10 mIU/mL.
- Anti-pneumococcal IgG concentrations for serotypes 1, 3, 4, 5, 6A, 6B, 7F, 9V, 14, 19A, 19F, 18C, and 23F.
- Anti-RV1 IgA concentrations.

Population-level summaries:

The following will be estimated at 28 days post-dose 2 of HIL-214 (administered at 6 months of age), comparing routine vaccines co-administered with HIL-214 to routine vaccines co-administered with placebo:

- Difference in percentages of subjects with anti-DT IgG concentration ≥ 0.1 IU/mL.
- Difference in percentages of subjects with anti-TT IgG concentration ≥ 0.1 IU/mL.
- Ratios of:
 - Anti-pertussis (FHA) IgG geometric mean concentrations (GMCs).
 - Anti-pertactin (PRN) IgG GMCs, and
 - Anti-toxoid (PTX) IgG GMCs.
- Difference in percentages of subjects with anti-poliovirus neutralizing antibody titers $\geq 1:8$, for poliovirus types 1, 2 and 3.
- Difference in percentages of subjects with PRP IgG concentration ≥ 0.15 μ g/mL.
- Difference in percentages of subjects with HBsAg Ig concentration ≥ 10 mIU/mL.
- Ratios of anti-pneumococcal IgG GMCs for serotypes 1, 3, 4, 5, 6A, 6B, 7F, 9V, 14, 19A, 19F, 18C, and 23F.
- Ratio of anti-RV1 IgA GMCs.

The analysis methods for the primary endpoints for the immunogenicity estimands are outlined in **Section 9.1.1.3**.

Intercurrent event strategies:

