9.1.1.2 Endpoints

All primary immunogenicity endpoints will be evaluated at Visit 4 and can be found in **Table 8**.

Table 8: Primary Immunogenicity Endpoints

Related Vaccine	Type of Endpoint	Endpoint
Infanrix Hexa/Vaxelis	Binary	Binary (yes/no) variable indicating anti-DT IgG concentration ≥ 0.1 IU/mL
		Binary (yes/no) variable indicating anti-TT IgG concentration ≥ 0.1 IU/mL
		Binary variable indicating anti-poliovirus neutralizing antibody titers $\geq 1:8$, for poliovirus types 1, 2 and 3
		Binary variable indicating anti-PRP IgG concentration ≥ 0.15 μ g/mL
		Binary variable indicating anti-HBsAg Ig concentration ≥ 10 mIU/mL
	Continuous	Anti-pertussis (FHA) concentrations
		Anti-pertactin (PRN) IgG concentrations
		Anti-toxoid (PTX) IgG concentrations
Prevnar 13	Continuous	Anti-pneumococcal IgG concentrations for serotypes 1, 3, 4, 5, 6A, 6B, 7F, 9V, 14, 19A, 19F, 18C, and 23F
Rotarix	Continuous	Anti-RV1 IgA concentrations

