9.1.1.3 Analysis Methods

A primary immunogenicity estimand and a supplementary estimand will be created for all of the endpoints outlined in **Table 8**. Analyses will be completed for the subgroups defined in **Section 7.4**.

For the primary immunogenicity estimands a complete case analysis will be performed, meaning any subjects with missing data for the parameter of interest will be excluded from the analysis.

For the supplementary immunogenicity estimands for the primary endpoints the missing data will be accounted for by reweighting the estimates using the method of inverse probability weighting. See **Section 7.5.1** for more details.

For the binary primary immunogenicity endpoints a standard summary for the categorical outcome will be presented as well as descriptive statistics for the continuous values. Further, the difference in percentage of subjects in the vaccine group with the event and the percentage of subjects in the

placebo group with the event will be evaluated. This will be presented along with a 95% CI calculated using the Miettinen and Nurminen [2] method as shown in **Section 5.4.1**.

For all continuous primary immunogenicity endpoints the geometric mean titer/concentration (GMT/GMC) with 95% CIs and geometric standard deviation (GSD) will be calculated. The GMRs between the vaccine group and the placebo group along with a 95% CI will be calculated using the analysis of variance (ANOVA) model with natural logarithm of antibody titer/concentration as the response variable and trial arm as a factor. Where country is used as a covariate (see **Section 7.3**) the adjusted GMs will also be presented. Further details can be found in **Section 5.4.3**.

For all primary immunogenicity parameters a reverse cumulative distribution curve will be produced, with titer/concentration on the x-axis and the percentage of patients below the titer value on the y-axis. All graphs will contain the two vaccine groups which will be overlaid.

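### The SAP's assay ceilings for diphtheria (0.005 IU/mL) and tetanus (0.041 IU/mL) lie below the 0.1 IU/mL endpoint threshold, so under its capping rule no infant can meet either primary endpoint

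*SAP*

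**What the plan says.** SAP 5.3.2.3 sits under the derived variables and opens its rules with "When summarizing immunogenicity assessments the following rules will apply". For high values the rule is "If a record is above the upper limit of quantification (ULOQ) then the ULOQ will be used in the summary". It makes no exception for endpoints defined by a threshold.

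Table 2 follows, introduced by "The following table gives the LLOD's, LLOQ's and ULOQ's for each of the parameters to be assessed on the study". In IU/mL, its DT row has LLOD 0.000010, LLOQ 0.000037 and ULOQ 0.005. Its TT row has LLOD 0.000038, LLOQ 0.00005 and ULOQ 0.041. The SAP's amendment details say the table was added in version 2.0 to document the relevant ranges, so it is current text.

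The endpoints are in SAP 4.2.1 and Table 8 (SAP 9.1.1.2), and match protocol 5.2.1:

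- DT: "Binary (yes/no) variable indicating anti-DT IgG concentration" of at least 0.1 IU/mL
- TT: "Binary (yes/no) variable indicating anti-TT IgG concentration" of at least 0.1 IU/mL

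For each binary endpoint SAP 9.1.1.3 promises that "a standard summary for the categorical outcome will be presented as well as descriptive statistics for the continuous values". SAP 7.4 restricts the hexavalent-vaccine antigens, which include DT and TT, to analysis by country.

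**The concern.** The limits and the thresholds carry the same unit, and the whole stated quantification range for DT and TT lies below the threshold. If the ceiling replaces every higher result before the comparison with 0.1 IU/mL, the endpoint is fixed at no for every infant.

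The trial's main question is whether HIL-214 interferes with the routine vaccines. A result of 0% in both arms with a difference of 0 has the form of a finding of no interference but carries no information. The continuous summaries of DT and TT would fail too, since no geometric mean could exceed 0.005 or 0.041 IU/mL.

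**Working it through.** The plan is descriptive and states no power or sample-size calculation that bears on this point, so there is no figure of its own to reproduce. The check applies the SAP's rules to its own limits.

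**Step 1: compare each ceiling with its threshold.** Limits are from SAP Table 2 and thresholds from SAP Table 8.

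| Endpoint | Threshold | LLOQ | ULOQ | Threshold / ULOQ | Can a capped value reach the threshold? |
|---|---|---|---|---|---|
| DT | 0.1 IU/mL | 0.000037 | 0.005 | 0.1 / 0.005 = 20.0 | No |
| TT | 0.1 IU/mL | 0.00005 | 0.041 | 0.1 / 0.041 = 2.44 | No |
| HBsAg | 10 mIU/mL | 10 | 14043.4 | 10 / 14043.4 = 0.0007 | Yes |
| PRP | 0.15 µg/mL | 0.15 | 28.55 | 0.15 / 28.55 = 0.005 | Yes |
| Polio 1, 2, 3 | 1:8 | N/A | N/A | no ceiling | Yes |

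HBsAg and PRP have an LLOQ equal to the threshold and a ULOQ far above it, as one would expect. The polio detection limit is printed as 2.50 with a log notation. Read as base 2, which is an assumption, it is 2^2.5 = 5.66, below 8. Only DT and TT conflict: 2 of 7 binary endpoints (DT, TT, three polio types, PRP, HBsAg).

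**Step 2: apply the substitution rules.** A value x becomes LLOD/2 if below the LLOD, (LLOD + LLOQ)/2 if between the LLOD and the LLOQ, x if within range, and the ULOQ if above it. The largest possible result is 0.005 for DT and 0.041 for TT. True values of 0.001, 0.01, 0.05, 0.1, 0.5, 1, 5 and 10 IU/mL were passed through the rules, and all eight were classed as no on both endpoints.

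**Step 3: the resulting comparison.** Both arms give 0/n, so the difference is 0.

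- SAP 5.4.1, formula (2), as printed, uses estimates under equal proportions. Both are 0, so the variance is 0 and the interval is 0 to 0.
- The Miettinen–Nurminen interval obtained by inverting the score test has limits ±d, with d = z²λ / (n + z²λ), λ = 2n/(2n − 1) and z² = 3.8415.
  - n = 50 per arm: z²λ = 3.8415 × 100/99 = 3.880, so d = 3.880 / 53.880 = 7.20 points.
  - n = 150 per arm: z²λ = 3.8415 × 300/299 = 3.854, so d = 3.854 / 153.854 = 2.51 points.

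The sizes 50 and 150 assume exactly 100 US infants (the protocol says at least 100), the other 300 in Panama, 1:1 allocation and no exclusions. On either formula the interval is centred on 0 and depends only on n, not on the data.

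**Step 4: what scale factor would remove the conflict?** If the limits are stated before dilution correction, the factor must be at least 20 for DT and at least 2.44 for TT. Neither document gives one.

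**Step 5: is the case provided for elsewhere?** SAP 7.5.1 has a rule for the situation where all observed cases are positive. It has none for all negative, which is what Table 2 would produce for DT and TT.

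**The case against.** The strongest objection is that the capping rule speaks of values used in a summary, whereas the endpoints are defined on the concentration itself. SAP 9 and 9.1.1.3 treat continuous and categorical outputs separately. One can therefore read the cap as applying only to the continuous summaries, with the 0.1 IU/mL comparison made on the uncapped record. If the laboratory supplies numeric values above the limit, the endpoint could then be derived.

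The reading is tenable, but the SAP nowhere states it. The rule covers immunogenicity summaries without exception, and counts above a threshold are among the summaries planned in SAP 9. If results arrive only as greater than the limit, they still cannot be classified against 0.1. Even on the favourable reading the DT and TT continuous summaries stay capped below the threshold, so Table 2 remains wrong for its purpose.

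The second objection is that the error would be noticed. SAP 9 tabulates the number of values above the ULOQ, SAP 9.1.1.3 asks for reverse cumulative distribution curves, and 0% responders after three doses of a licensed vaccine would look like a processing error. There is also no margin or success rule that would turn the result into an automatic claim. This stands as a comment on likelihood: a silent false result is less probable than a late repair. But a repair after results are seen, on a primary endpoint, is what a pre-specified plan should prevent.

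Third, the pertussis rows have no threshold, so nothing there is in demonstrated conflict. That is right, and for them only a check is asked.

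**Conclusion.** The concern holds and should be fixed before the analysis. As written, the SAP's rule and limits make DT and TT non-response certain for every infant, in both arms, both countries, and both the primary and supplementary estimands. The threshold exceeds the ceiling by a factor of 20 for DT and 2.44 for TT.

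The 0% result rests on applying the cap before the yes/no classification, which is what the text says in the absence of any exemption. The defect in Table 2 does not depend on that order, because the capped continuous summaries are wrong either way. The finding is an inconsistency inside the SAP. Whether the laboratory can quantify 0.1 IU/mL cannot be judged from the documents, and a scale or unit slip in the table is a possible explanation.

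**What to change.** 1. Replace the DT and TT limits in SAP Table 2 with limits on the scale of the reported serum concentrations, taken from the assay report, and state that scale.
2. Add one sentence to SAP 5.3.2.3: yes/no variables are derived from the reported concentration before any substitution for LLOD, LLOQ or ULOQ.
3. Add a check that, for each threshold endpoint, the ULOQ exceeds the threshold and the LLOQ does not exceed it.
4. Check the FHA, PRN and PT rows. They are in the same unit and feed geometric mean ratios. If their ceilings were also on the wrong scale, capping in both arms would pull those ratios towards 1.

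The cost is a table correction and a derivation sentence in a SAP amendment before database lock, with no protocol amendment. SAP 7.6.2 withholds only HIL-214 immunogenicity data from the blinded statistical team before lock, so the form of the DT and TT records could be checked on blinded data first.
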